3.8.8.5 HOMA-IR

Blood samples for determination of fasting plasma glucose and insulin levels will be collected according to the [Schedule of Events](#). Values will be used in the Homeostatic Model Assessment to estimate insulin resistance (HOMA-IR).[\(34,35\)](#)

The HOMA-IR equation is:

$$\text{HOMA-IR} = (\text{FPI} \times \text{FPG})/22.5,$$

where FPI is fasting plasma insulin concentration (mU/L) and FPG is fasting plasma glucose (mmol/L).

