Clinical Laboratory Assessments

Complete blood count, serum chemistry panel, urinalysis, coagulation panel, UACR (urine albumin [mg/dL] / urine creatinine [g/dL]), estimated glomerular filtration rate (eGFR; by the Chronic Kidney Disease Epidemiology Collaboration [CKD-EPI] creatinine equation), hemoglobin A1c, Homeostatic Model Assessment to estimate insulin resistance (HOMA-IR), [REDACTED], urine pregnancy, and screens for hepatitis, human immunodeficiency virus, and drugs of abuse.

Hemodynamics and Vital Signs

Seated and standing BP (systolic and diastolic) and pulse measurements by automated office blood pressure (AOBP), ambulatory BP (systolic and diastolic) and pulse monitoring, respiratory rate, oral temperature. Orthostatic (standing minus seated) measurements will be calculated for BPs and pulse.

[REDACTED]

[REDACTED]

Other

Adverse-event recording, electrocardiograms (ECGs), physical examinations, concomitant medications.

Pharmacokinetics

Plasma IW-1973 concentrations will be measured.

[REDACTED]

[REDACTED]

[REDACTED]

[REDACTED]

[REDACTED]

[REDACTED]

[REDACTED]

[REDACTED]

Study Endpoints

Primary Endpoints

- Primary Safety: Incidence of TEAEs and study drug-related TEAEs
- Primary Efficacy: Change from baseline in UACR over Weeks 8 and 12

Statistical Methods

Sample Size Determination

Using an estimate of standard deviation of 0.67, a sample size of 40 patients per treatment group would provide approximately 80% power to detect a mean between-group difference of -0.376 units in change from baseline in log-transformed UACR over 12 weeks, with a one-sided significance level of 0.05 for at least 1 dose versus placebo comparison. This difference corresponds to a 31% between-group reduction of geometric mean change from baseline in UACR. Assuming a drop-out rate of 20%, approximately 150 patients will be randomly assigned in a 1:1:1 ratio (approximately 50 patients per treatment group) to 20 mg IW-1973, 40 mg IW-1973, or placebo.

Analysis Populations

Safety Population: The Safety Population will consist of all randomized patients who receive at least 1 dose of study drug. Patients in this population will be evaluated according to the treatment they actually received.

Intent-to-Treat (ITT) Population: The ITT Population will consist of all randomized patients who receive at least 1 dose of study drug. Patients in this population will be evaluated according to the treatment group they were assigned at Randomization.

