3. Patient has type 2 diabetes diagnosed by a physician or nurse practitioner ≥ 6 months before the Screening Visit, has been on ≥ 1 antihyperglycemic medication for ≥ 12 weeks preceding the Randomization Visit, and has been on a stable regimen (ie, same drug and same dose) of ≥ 1 antihyperglycemic medication for ≥ 28 days preceding the Randomization Visit.
(Modification of short-acting insulin throughout the Screening Period will not affect eligibility.)
4. Patient has been on a stable regimen (ie, same drug and dose) of an angiotensin-converting enzyme inhibitor (ACEi) or an angiotensin receptor blocker (ARB), for ≥ 28 days preceding the Randomization Visit and is expected to remain on their regimen through the Follow-up Visit. (Note: These medications may be modified during the study if medically necessary.)
5. If patient is on medications for hypertension, regimen (drug[s] and dose[s]) must be stable for ≥ 28 days preceding the Randomization Visit and is expected to remain stable through the Follow-up Visit. (Note: Medications for antihypertension may be modified during the study if medically necessary.)
6. Patient has the following:
 - a. Estimated glomerular filtration rate (eGFR) 30 to 75 mL/min/1.73 m² by the Chronic Kidney Disease Epidemiology Collaboration (CKD-EPI) creatinine equation (1) at the Screening and Baseline Visits
 - b. Urine albumin creatinine ratio (UACR) >200 mg/g and <5000 mg/g at the Screening and Baseline Visits (at the Baseline Visit, the mean of the 2 first morning void tests will be used to determine eligibility)
 - c. Serum albumin >3.0 g/dL at the Screening and Baseline Visits
 - d. Hemoglobin A1c (HbA1c) $\leq 12\%$ at the Screening and Baseline Visits
 - e. Systolic blood pressure (BP) of 110 to 160 mm Hg based on the average of 3 seated automated office blood pressure (AOBP) measurements at the Screening and Baseline Visits
7. Female patient must be postmenopausal (no menses for ≥ 12 consecutive months); surgically sterile (ie, bilateral oophorectomy, hysterectomy, or tubal sterilization [tie, clip, band, or burn]); must agree to completely abstain from heterosexual intercourse; or, if heterosexually

active, must agree to use 1 of the following methods of birth control from the date she signs the ICF until 60 days after the final dose of study drug:

- a. Progesterone implant or an intrauterine device (IUD)

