3.4 STUDY POPULATION

3.4.1 Study Population Description

This study will enroll approximately 150 adult patients with type 2 diabetes mellitus and albuminuria at multiple sites in the US. Patients must have type 2 diabetes diagnosed by a physician or nurse practitioner no fewer than 6 months before the Screening Visit and must have been taking at least 1 medication specifically for control of glycemia, either oral or injectable, for

at least 12 weeks before the Randomization Visit and have been on a stable regimen (ie, same drug and same dose) for at least 28 days preceding the Randomization Visit. To be eligible, patients must have a hemoglobin A1c (HbA1c) level of $\leq 12\%$. At Screening, patients must also have an eGFR of 30 to 75 mL/min/1.73 m² (Chronic Kidney Disease Epidemiology Collaboration [CKD-EPI] creatinine equation), UACR >200 and <5000 mg/g, and serum albumin >3.0 g/dL. In addition, patients must have been on a stable regimen (ie, same drug and dose) of an ACEi or an ARB, for at least 28 days before the Randomization Visit. Patients must have systolic BP of 110 to 160 mm Hg, and if taking medications for hypertension, regimen must be stable for at least 28 days preceding the Randomization Visit. Patients with known nondiabetic renal disease are not eligible.

Refer to [Eligibility Criteria](#) for full inclusion and exclusion criteria.

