3.5.7 Prior and Concomitant Therapy

At the Screening Visit, the following information will be recorded for each patient:

- All medications the patient is taking (ongoing)
- All prior medications taken during the 30 days before the Screening Visit

Beginning at the Screening Visit, any medication or change in medication taken by a patient during the study will be documented in the source documents and the eCRF along with the start and stop date and the reason for use.

Patients will be on a stable regimen of at least 1 antihyperglycemic medication and an ACEi or an ARB (see [Inclusion Criteria](#) for details), which may be modified during the study if medically necessary. Patients may be on a stable regimen of medication(s) for hypertension, which may be modified during the study if medically necessary. Permitted concomitant medications should be taken at the same time each day and may be taken at the same time as study drug.

Pharmacological stimulation of sGC by IW-1973 produces an increase in cGMP production. Concomitant administration of IW-1973 with an angiotensin receptor neprilysin inhibitor (ie, sacubitril/valsartan) should be allowed with caution as neprilysin inhibition results in increased cGMP concentrations via protection of natriuretic peptides.

Prohibited medications and supplements are listed in Sections [3.6](#) and [Appendix 1](#).

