3.8.8 Clinical Laboratory Tests

Blood and urine samples for clinical laboratory tests will be collected according to the [Schedule of Events](#). Except for the Screening Visit, patients should fast for at least 8 hours before sample collections.

The clinical laboratory evaluations will include the serum chemistry, hematology (complete blood count [CBC]), coagulation, UA, and additional tests as presented in [Table 4](#).

Table 4. Clinical Laboratory Tests

Serum Chemistry	Hematology (CBC)	Urinalysis
Albumin	Hematocrit	Color and appearance
Alkaline Phosphatase	Hemoglobin	pH and Specific Gravity
ALT	Platelet count	Bilirubin
AST	MPV	Glucose
Bicarbonate	RBC count	Ketones
BUN	WBC count	Leukocytes
Calcium	WBC differential	Nitrites
Chloride	(% & absolute):	Occult blood
Cholesterol	Basophils	Protein
Creatinine	Eosinophils	Urobilinogen
GGT	Lymphocytes	Microscopic
Glucose	Monocytes	Including bacteria, RBCs, WBCs per HPF if dipstick is abnormal
HDL-c	Neutrophils	
LDH	RBC indices	
LDL-c (calculated)	MCH	Additional blood tests
Magnesium	MCHC	Hemoglobin A1c
Phosphorus	MCV	Fasting plasma glucose
Potassium	RDW	Fasting plasma insulin
Sodium		
Total Bilirubin	Coagulation	Additional urine tests
Total Protein	aPTT	Urine albumin & creatinine for UACR*
Triglycerides	Prothrombin time	Urine cotinine
Uric acid	INR	

ALT=alanine aminotransferase; aPTT=activated partial thromboplastin time; AST=aspartate aminotransferase; BUN=blood urea nitrogen; CBC=complete blood count; GGT=gamma glutamyl transferase; HPF=high power field; INR=International Normalized Ratio; LDH=lactate dehydrogenase; MCH=mean corpuscular hemoglobin; MCHC=mean corpuscular hemoglobin concentration; MCV=mean corpuscular volume; MPV=mean platelet volume; RBC=red blood cell; RDW=red blood cell distribution width; UACR=urine albumin-creatinine ratio; WBC=white blood cell.

* At the Screening Visit, a single urine sample, which may not be first void, may be collected. Thereafter, samples should be 2 first-void urine samples collected on the 2 consecutive mornings before each scheduled study visit. Patients will be supplied with specimen collection supplies at the preceding study visit.

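### HOMA-IR is derived from measured fasting insulin with no visible restriction, although insulin-treated patients are eligible, and in those patients it does not estimate insulin resistance

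*Protocol*

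**What the plan says.** **Derivation.** Protocol Section 3.8.8.5 gives the purpose of the fasting glucose and insulin samples: "Values will be used in the Homeostatic Model Assessment to estimate insulin resistance". The formula is (FPI × FPG)/22.5, where FPI is the measured plasma insulin in mU/L and FPG the plasma glucose in mmol/L. Section 3.9 lists these samples at the Baseline, Week 1, Week 4, Week 8 and End of Treatment Visits. The synopsis lists HOMA-IR among the laboratory assessments without qualification.

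**Who is admitted.** Inclusion criterion 3 adds the note "Modification of short-acting insulin throughout the Screening Period will not affect eligibility". Section 3.4.1 accepts "at least 1 medication specifically for control of glycemia, either oral or injectable". No exclusion criterion names insulin.

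**What may change.** Inclusion criterion 3 asks for stability of at least one glucose-lowering drug, not of all of them. Section 3.5.7 says of the background regimen, "which may be modified during the study if medically necessary".

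**Sampling conditions.** Section 3.8.8 says that, except at Screening, "patients should fast for at least 8 hours before sample collections". Section 3.5.7 asks that permitted medication be taken at a constant time of day and allows it together with study drug. Neither sentence places insulin before or after the blood sample.

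**The concern.** HOMA-IR reads a high product of fasting insulin and fasting glucose as resistance. That reading supposes that the measured insulin is the patient's own secretion in response to the measured glucose. In a patient who injects insulin, part of the circulating insulin is set by a prescription instead. The index can then change because the dose, the product or the time since injection changed.

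The protocol knowingly admits such patients and still presents the formula as an estimate of insulin resistance. Anyone who follows Section 3.8.8.5 literally would mix interpretable values with values that cannot be read that way. At stake is the meaning of one metabolic measure, not the albuminuria or adverse-event results.

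**Working it through.** The protocol states no figure for HOMA-IR that could be reproduced. The check therefore has two parts: whether any visible text protects the index, and how the formula behaves when injected insulin is present.

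**1. Search for a safeguard**

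- Restriction to patients not on insulin: none in Section 3.8.8.5, the synopsis or Section 5.9.
- Rule on insulin before sampling: none. The fast concerns food. Section 3.8.6 does set medication timing for another measurement, since predose blood pressure comes before oral and antihypertensive medication. Nothing comparable is set for the insulin sample.
- A measure of the patient's own secretion, such as C-peptide: none visible in Table 4.
- Stratification by insulin use: none. Randomization is stratified by eGFR only.

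**2. If the assay detects the injected product**

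Let E be the patient's own fasting insulin and X the injected insulin that the assay measures, both assumed.

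HOMA-IR = (E + X) × FPG / 22.5, so the index is multiplied by (E + X)/E at any fixed FPG.

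With assumed E = 10 mU/L and FPG = 8 mmol/L:

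| X (mU/L) | HOMA-IR | Factor |
|---|---|---|
| 0 | 10 × 8/22.5 = 3.56 | 1 |
| 5 | 15 × 8/22.5 = 5.33 | 1.5 |
| 10 | 20 × 8/22.5 = 7.11 | 2 |
| 20 | 30 × 8/22.5 = 10.67 | 3 |
| 40 | 50 × 8/22.5 = 17.78 | 5 |

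Over assumed E of 5 to 15 mU/L, the factor runs from (15 + 5)/15 = 1.33 to (5 + 40)/5 = 9. These figures show only how strongly the formula responds to measured insulin. Glucose is held fixed, so they do not describe a patient whose resistance is known to be unchanged.

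A dose increase would normally also lower glucose. Assume that measured FPI goes from 15 to 25 mU/L and FPG from 9 to 7.5 mmol/L:

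- before: 15 × 9/22.5 = 6.00
- after: 25 × 7.5/22.5 = 8.33, which is 8.33/6.00 = 1.39, or +39%

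The index appears to worsen while glucose improves.

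**3. If the assay does not detect the injected product**

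Measured FPI is then E alone, while the glucose reflects E + X. Take the same assumed fall in glucose with measured FPI unchanged at 15 mU/L:

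- after: 15 × 7.5/22.5 = 5.00, which is 5.00/6.00 = 0.83, or −17%

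The same kind of treatment change pushes the index up in one case and down in the other. The protocol does not describe the assay, so even the direction of the artefact is unknown.

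**4. Does change from baseline remove it?**

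Only if the injected contribution stayed constant. Inclusion criterion 3 allows short-acting insulin to change through screening, and Section 3.5.7 allows changes after randomization. Constancy is therefore not assured.

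**The case against.** The strongest objection is that Section 3.8.8.5 only defines an index, and that who enters an exploratory summary is a matter for the statistical analysis plan. Section 5.1 defers further statistical detail to that plan, which is not available here. The exploratory objectives and endpoints are blacked out, so it cannot be seen whether HOMA-IR is a formal endpoint, whether it is restricted there, or whether the mixed model of Section 5.9 applies to it. All of that stands. It follows that use in every patient is inferred from the absence of a restriction; the protocol does not say it. What remains is that the protocol itself states the formula and its purpose, and that statement fails for a subgroup it admits.

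A second objection is that the validity of HOMA-IR under injected insulin is outside knowledge and depends on an assay that is not described. The assay point stands as a limit on direction and size. It does not rescue the index, because both branches in the working separate measured insulin from the insulin acting on the glucose.

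Third, a reader might infer that the comparison between arms is biased. The documents do not support that. The trial is randomized and double-blind, so baseline insulin use is balanced in expectation. Section 1.4.1 reports lower fasting glucose on IW-1973 in a diabetic rat model, which makes different insulin changes by arm conceivable, but nothing shows them in patients.

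Fourth, a reader might take a three- or five-fold inflation as the expected error. It is not: the insulin values are assumed and glucose is held fixed.

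**Conclusion.** The point holds as a minor one. Section 3.8.8.5 derives HOMA-IR from measured fasting insulin with no visible restriction, while insulin-treated patients are eligible and may change regimen on study. In them the index does not estimate insulin resistance, whichever way the assay behaves.

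The size for the trial cannot be stated, because the share of insulin users is not given. For an individual, the assumed ranges give a factor of 1.33 to 9 at fixed glucose. The two dose-change examples give +39% and −17%. All rest on assumed insulin and glucose values.

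The conclusion is confined to the meaning of HOMA-IR in insulin users. It is not a finding of bias between arms. The primary endpoints, albuminuria over Weeks 8 and 12 and treatment-emergent adverse events, do not use the index, and neither does the sample size.

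**What to change.** State in Section 3.8.8.5 that HOMA-IR will be analysed and interpreted only in patients not taking insulin at baseline. This subgroup is defined before randomization, so the comparison between arms within it stays a randomized one.

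For patients in this subgroup who start insulin during the study, report their number by arm. Show the HOMA-IR result with and without their values after the start, as a sensitivity analysis. Simply discarding those values would condition on an event after randomization and could itself distort the comparison.

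The cost is small. Section 3.5.7 already has medications and changes recorded with dates, and no visit, sample or treatment rule needs to change. Fasting glucose and HbA1c are already collected and remain available for all patients. The downside is a smaller sample for a non-primary measure, by an amount that depends on the unstated share of insulin users.

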3.8.9 Adverse Events

All patients will be monitored for AEs throughout the study. All AEs will be recorded in accordance with the procedures outlined in this section.

An AE is any untoward medical occurrence in a patient or clinical investigation subject administered a pharmaceutical product and which does not necessarily have to have a causal relationship with this treatment.

An AE, therefore, can be any unfavorable and unintended sign (including an abnormal laboratory finding, for example), symptom, or disease temporally associated with the use of a medicinal product, whether or not considered related to the medicinal product.

An AE includes, but is not limited to, the following:

- Any unfavorable changes in general condition
- Any clinically significant worsening of a preexisting condition
- Any intercurrent diseases and accidents

Note: A procedure is not an AE, but the reason for a procedure may be an AE.

3.8.9.1 Causality Assessment

For all AEs, the Investigator must provide an assessment of causal relationship to study drug.

The causality assessment must be recorded in the patient's source documentation and on the AE page of the subject's eCRF. Causal relationship must be assessed according to the following:

Related: An event where there is a reasonable possibility of a causal relationship between the event and the study drug

Unrelated: Any other event

3.8.9.2 Severity Assessment

The Investigator will provide an assessment of the severity of each AE by recording a severity rating in the patient's source documentation and on the AE page of the patient's eCRF. *Severity*, which is a description of the intensity of manifestation of the AE, is distinct from *seriousness*, which implies a patient outcome or AE-required treatment measure associated with a threat to life or functionality. Severity will be assessed according to the following scale:

Mild: A type of AE that is usually transient and may require only minimal treatment or therapeutic intervention. The event does not generally interfere with usual activities of daily living.

Moderate: A type of AE that is usually alleviated with additional specific therapeutic intervention. The event interferes with usual activities of daily living, causing discomfort but poses no significant or permanent risk of harm to the research participant.

Severe: A type of AE that interrupts usual activities of daily living, or significantly affects clinical status, or may require intensive therapeutic intervention.

3.8.9.3 Serious Adverse Events

An SAE is defined as any AE occurring at any dose that results in any of the following outcomes:

- Death
- Life-threatening: the patient was at immediate risk of death from the reaction as it occurred (ie, it does not include a reaction that hypothetically might have caused death if it had occurred in a more severe form)
- Hospitalization or prolongation of existing hospitalization
- Persistent or significant disability/incapacity: a substantial disruption of a person's ability to conduct normal daily functions
- Congenital anomaly/birth defect
- Important medical events: events that may not result in death, be life threatening, or require hospitalization. Such an event may be considered serious when, based on appropriate medical judgment, it may jeopardize the subject and may require medical or surgical intervention to prevent 1 of the outcomes listed in this definition. Examples of such medical events include allergic bronchospasm requiring intensive treatment in an emergency department or at home, blood dyscrasias or convulsions that do not result in inpatient hospitalization, or the development of drug dependency or drug abuse.

Emergency room visits that do not result in admission to the hospital should be evaluated for 1 of the other serious outcomes (eg, life-threatening, other serious [medically important] event).

3.8.9.4 Recording Adverse Events

Adverse events will be collected and recorded from the time the patient signs the ICF at the Screening Visit through the Follow-up Visit. All AEs, regardless of the assumption of a causal relationship with study procedures or study medication, must be recorded in the patient's source documentation and subsequently on the appropriate AE page of the patient's eCRF. This record includes AEs the patient reports spontaneously, those observed by the Investigator, and those elicited by the Investigator in response to open-ended questions during the study, such as "Have you had any health problems since your last visit?"

For every AE, the Investigator must:

- Provide an assessment of the severity, causal relationship to the study medication, and seriousness of the event
- Document all actions taken with regard to the study medication (ie, no action taken, treatment temporarily interrupted, or treatment discontinued)
- Detail any other treatment measures taken for the AE, including concomitant medications and/or procedures

Pretreatment AEs will be collected from the time the patient signs the ICF until the patient receives study drug. Pretreatment AEs will be captured in the patient's source documentation but will only be entered for randomized patients on the AE page of the patient's eCRF.

Laboratory abnormalities and changes in vital signs, physical examination findings, and 12-lead ECG parameters should be considered AEs and reported on the AE page of the patient's eCRF if the Investigator considers them clinically significant and/or they necessitate intervention.

Any medical condition that is present when a patient is screened and does not worsen in severity and/or frequency should be reported as Medical History and not as an AE. However, if the condition does deteriorate in severity and/or frequency at any time during the study, it should be reported as an AE.

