Follow-up Period: The Follow-up Period will begin immediately after the End of Treatment Visit and will last for 28 (± 3) days. At the Follow-up Visit on Day 115 (± 3), patients will return to the clinic for final study assessments (see [Schedule of Events](#)).

Study Schematic

Study Drug Administration

During Week 1, patients will take study drug BID ($2 \times$ /day), 1 tablet in the morning and 1 tablet approximately 12 hours later in the evening, preferably at approximately the same times each day. From the Week 1 Visit (Day 8 ± 1) on, patients will take study drug QD ($1 \times$ /day), 2 tablets in the morning, preferably at approximately the same time each day. Patients should take study drug with water, may take study drug with or without food, and, for QD dosing, may swallow tablets together, if desired. On study visit days, patients will receive their study drug dose in the clinic (on Randomization Day, patients will receive only their morning dose in the clinic). Study visits should be scheduled in the morning to accommodate regular dosing schedule.

Duration of Treatment

Patients will receive daily study drug for up to 90 days. Total patient participation will be 131 to 163 days, including the Screening, Treatment, and Follow-up Periods.

Dose Reduction

Per Investigator discretion, on a per-patient basis, dose may be reduced by half, ie, from 2 tablets daily to 1 tablet daily (in the morning). Each patient's dose may only be reduced once and may not be increased after reduction. Investigators should notify the Medical Monitor of all decisions to dose reduce on a per-patient basis.

Individual Stopping Criteria and Data Monitoring Committee Reviews

If any events included in the table below are reported during the study and are judged to be both study drug related and a serious adverse event (SAE; per causality and SAE definitions in the protocol), individual stopping criteria or Data Monitoring Committee (DMC) review will be triggered as described below. The inclusion of these AEs is based on the clinical experience with IW-1973, the prescribing information for riociguat, and the patient population for this study.

Treatment-emergent, Study Drug-related SAE Category	# of patients to trigger DMC review
Renal failure (eGFR <15 mL/min/1.73 m ² ; dialysis or renal transplant indicated)	2
Spontaneous bleeding events (eg, hemoptysis, subarachnoid or subdural hemorrhage, hematemesis, hematochezia)	2

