2. STUDY OBJECTIVES

Primary

- To assess the safety and tolerability of oral IW-1973 when administered daily for approximately 12 weeks to adult patients with type 2 diabetes mellitus with albuminuria who are on a stable regimen of renin-angiotensin system inhibitors
- To evaluate the effect of oral IW-1973 on renal function when administered daily for approximately 12 weeks to adult patients with type 2 diabetes mellitus with albuminuria who are on a stable regimen of renin-angiotensin system inhibitors

Exploratory

[figure not shown]

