3.5.4.2 Dose Reduction

Per Investigator discretion, on a per-patient basis, dose may be reduced by half, ie, from 2 tablets daily to 1 tablet daily (in the morning). Each patient's dose may only be reduced once and may not be increased after reduction. Investigators should notify the Medical Monitor of all decisions to dose reduce on a per-patient basis.

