4. STUDY ENDPOINTS

4.1 PRIMARY ENDPOINTS

4.1.1 Primary Safety

- Incidence of TEAEs and study drug-related TEAEs

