5.3 ANALYSIS POPULATIONS

The following populations will be defined for this study:

- **Safety Population:** The Safety Population will consist of all randomized patients who receive at least 1 dose of study drug. Patients in this population will be summarized according to the treatment they actually received.
- **Intent-to-Treat (ITT) Population:** The ITT Population will consist of all randomized patients who receive at least 1 dose of study drug. Patients in this population will be evaluated according to the treatment group they were assigned to at Randomization.
- **PK Population:** The PK Population will consist of all randomized patients who receive at least 1 dose of study drug and have at least 1 postdose PK parameter assessment.
- **Per-Protocol (PP) Population:** The PP Population will consist of all ITT patients who did not have any major protocol deviations or dose reduction.

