7.1 GENERATION OF STUDY RECORDS

Ironwood or its designated representative will conduct a study site visit to verify the qualifications of each Investigator, inspect study site facilities, and inform the Investigator of responsibilities and procedures for ensuring adequate and correct study documentation.

The Investigator is required to prepare and maintain adequate and accurate case histories designed to record all observations and other data pertinent to the study for each study patient. All information recorded in the eCRFs for this study must be consistent with the patient's source documentation.

During the course of the study, the Clinical Site Monitor will make study site visits to review protocol compliance, compare eCRFs and individual patient's medical records, assess drug accountability (in a blinded manner), and ensure that the study is being conducted according to pertinent regulatory requirements. All eCRFs will be verified with source documentation. The review of medical records will be performed in a manner that ensures patient confidentiality is maintained.

The Clinical Site Monitor will discuss instances of missing or uninterpretable data with the Investigator for resolution. Any changes to the study data will be made to the eCRF and documented via an electronic audit trail associated with the affected eCRF.

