7.3 ELECTRONIC CASE REPORT FORMS AND DATA MANAGEMENT

All data relating to the study will be recorded in the patient's source documentation and eCRF to be provided by Ironwood or designee via the electronic data capture (EDC) system. Source documentation supporting the eCRF data should indicate the patient's participation in the study and should document the dates and details of study procedures, AEs, all observations, and patient status. The Investigator is responsible for verifying that all data entries on the eCRFs are accurate and correct and ensuring that all data are entered in a timely manner, as soon as possible after the information is collected. An explanation should be provided for any missing data. The Investigator must provide through the EDC system his or her formal approval of all the information in the eCRFs and changes to the eCRFs to endorse the final submitted data for each patient.

Ironwood will retain the final eCRF data and corresponding audit trails. A copy of the final archival eCRF in the form of a compact disc or other electronic media will be placed in the Investigator's study file.

A record of screen failures and pretreatment failures will be maintained for patients who do not qualify for enrollment, including the reason for the failure.

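### Does leaving dose reduction out of the action-taken list for adverse events lose information the trial needs?

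*Protocol*

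**What the plan says.** Section 3.8.9.4 sets out what the investigator must do for each adverse event. One duty is to "Document all actions taken with regard to the study medication (ie, no action taken, treatment temporarily interrupted, or treatment discontinued"). The next duty in that section covers other treatment measures, such as concomitant medication or procedures.

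Section 3.5.4.2 says that, at the investigator's discretion, the "dose may be reduced by half, ie, from 2 tablets daily to 1 tablet daily (in the morning"). The Synopsis has the same provision, and both add the limit: "Each patient's dose may only be reduced once and may not be increased after reduction". Both also ask that the Medical Monitor be told of every such decision.

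Reduction appears once more in the analysis sections. Section 5.3 states: "The PP Population will consist of all ITT patients who did not have any major protocol deviations or dose reduction".

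On records, Section 7.3 requires study data to be held in both source documents and the eCRF, and says that source documentation "should document the dates and details of study procedures, AEs, all observations, and patient status". Section 7.1 adds: "All eCRFs will be verified with source documentation".

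**The concern.** The list in Section 3.8.9.4 is introduced by ie, not eg, so it reads as complete. A dose reduction fits none of its three entries. It is not the absence of action. It is not a discontinuation, because the patient stays on drug. It is not a temporary interruption, because dosing continues and the dose may not go back up.

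This seems to matter because the first primary objective is "To assess the safety and tolerability of oral IW-1973 when administered daily for approximately 12 weeks". An event severe enough to halve the dose says something about tolerability. In the high-dose arm, a reduction from two 20 mg tablets to one takes the patient from 2 × 20 = 40 mg to 1 × 20 = 20 mg a day, which is the daily amount in the low-dose arm (2 × 10 = 20 mg). Section 5.10.1 summarises by arm the events leading to discontinuation of study drug. A reader might want events leading to reduction beside them. If the adverse event page offered only the three listed answers, the link between an event and a reduction would have to be rebuilt from dates or source notes, which is less reliable than a direct entry.

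**Working it through.** The question is one of wording and data flow, so the check compares the sections and follows each possible use of the missing entry.

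**1. Count of actions.** The protocol mentions four possible actions on study drug: none, interruption, reduction and discontinuation. Section 3.8.9.4 lists three, so 4 − 3 = 1 is missing, and that one is reduction. Each patient can have at most one reduction.

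**2. Can both sections be obeyed together?** Section 3.5.4.2 permits a reduction. Section 3.8.9.4 does not forbid or deny it, and its operative words require documentation of all actions on study medication. An investigator who reduces a dose because of an event satisfies both sections by recording the reduction. The parenthesis is incomplete, but the two sections do not contradict each other.

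**3. Where else is a reduction captured?** Section 7.3 requires study data in source and eCRF. Section 3.5.4.2 requires notification of the Medical Monitor. Section 3.5.5 bases compliance on tablet counts, which fall when a patient takes one tablet a day where two were planned. None of these names a dose-reduced option on the adverse event page, but together they make it unlikely that a reduction goes unrecorded.

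**4. Which stated results use the action taken for an event?**

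| Stated result | Uses a dose-reduction entry on the adverse event record? | Effect of the omission |
|---|---|---|
| Primary safety endpoint (4.1.1): "Incidence of TEAEs and study drug-related TEAEs" | No. Section 5.10.1 defines these events by onset or worsening after study drug, and relatedness is a separate assessment (3.8.9.1) | 0 |
| Adverse event summaries and listings (5.10.1) | Only discontinuation is used, and it is on the list | 0 |
| Primary efficacy analysis in the ITT population (5.9) | No | 0 |
| Per-protocol membership (5.3) | Needs to know that a reduction occurred, not which event prompted it; dosing records supply this | 0, provided reductions are recorded as step 3 describes |
| Individual stopping and DMC triggers (3.7, 5.13) | No. They depend on category, seriousness and relatedness | 0 |

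**5. What remains?** One possible product: a table by arm of events leading to reduction. The protocol does not plan it. Whether it could be produced directly depends on the answer options on the eCRF, which the protocol does not reproduce. Section 7.4 refers to the eCRFs and separate instructions for completing them, and field options belong there. If the form already offers a dose-reduced option, the number of patients affected is 0. If it does not, the number cannot be derived, because the protocol gives no expected rate of reductions and does not say how many would be prompted by adverse events.

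**The case for a change.** The strongest case for a change is that an SAP can decide which tables to produce but cannot create a link that was never recorded. What the investigator records is set by the protocol, and this list is worded as complete. Tolerability by dose is a question the trial asks: Section 3.5.3 chose 20 mg partly because it had fewer adverse events in the earlier multiple-dose study. Adding two words and checking one form field would cost almost nothing before data collection, and reconstruction afterwards is less reliable.

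Part of this stands. The omission is real, and no other section supplies an adverse-event-level entry for reduction. A sponsor tidying the document would sensibly complete the list. What does not stand is the step from an incomplete parenthesis to lost information. That step assumes that the eCRF copies the list literally and that the requirement to record all actions is ignored. The protocol supports neither assumption. Nor does Section 3.5.4.2 tie reductions to adverse events; it leaves them to the investigator's discretion.

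**Conclusion.** No change to the plan is needed. The list in Section 3.8.9.4 has a clerical gap, one action of four, which its own instruction to record all actions already covers. No endpoint, population definition or planned analysis changes, and an analyst who follows the protocol as written reaches the same results.

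This rests on two assumptions. First, reductions are entered in source and eCRF, as Section 7.3 requires, so that the per-protocol population can be built. Second, no stated analysis needs the reason for a reduction at the level of the individual event, which is true of the protocol text. The wording finding is certain. The practical consequence cannot be judged without the eCRF; at most it would be a less direct description of tolerability.
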